3.10.3.5 Unified Parkinson's Disease Rating Scale (UPDRS) – Appendix XII

The UPDRS assesses motor and functional abilities of the subjects. ⁴⁵ The total UPDRS will be completed (defined for this study as the sum of Parts I, II, III, and IV (I-Mentation, behavior, and mood section; II-Activities of Daily Living (ADL); III-motor section; and IV-complications section) will be completed by history and examination. The UPDRS parts III and IV evaluation will be conducted by a trained neurologist or other senior trained research staff with at least 10 years' experience in conducting the UPDRS. All attempts will be made to ensure that the same trained research staff member performs the UPDRS parts III and IV at all visits for each subject and at approximately the same time of the day and time following administration of medication. The UPDRS parts I and II may be completed by trained research staff as delegated by the PI.

3.10.3.6 Excessive Salivation Question (Unified Parkinson's Disease Rating Scale Question 6 - UPDRS-6) – Appendix XII

This is question 6 on the UPDRS⁴⁵ which refers specifically to excessive salivation. It is rated 0-4 and can be self-administered.

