7.4 Data summary

Data will be collected on case report forms for each participant at each visit and doubleentered into a secure study database. A quality check of data will occur after the first five records and prior to analysis, looking for out-of-range values and inconsistent data. The study statistician will conduct additional quality checks prior to data analyses including consistency between rounds of data entry, checking for duplicate entries, truncation of data, out-of-range values, inconsistent data and amount of missing data. Data discrepancies will be resolved and documented prior to data analysis. Missing data will not be imputed. After quality checks have been completed, a final database will be created with proper formatting and any appropriate mathematical algorithms applied including change from randomization visit (Visit 3).

Descriptive summaries will be generated for all demographic and clinical variables by study visit and treatment group including number, mean, median, standard deviation, minimum and maximum for continuous variables and number and percent for categorical variables. Summaries for change from randomization visit will also be generated. The number and screening/baseline characteristics of withdrawn participants will be recorded.

Subgroups for analyses may include treatment group, time point/study visit, age group and sex. A significance level of 0.05 will be used throughout with no adjustment for multiplicity. Normality will be tested throughout using the Shapiro-Wilk test. All analyses will be conducted on the final dataset in SAS version 9.3 or higher.

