7.4.1 Summary of primary outcome data

The primary objective of this experimental protocol is to assess cognitive tolerability of mirabegron while treating OAB symptoms in patients with PD and CI. The hypothesis is that mirabegron will not impact cognitive impairment. The goal is to demonstrate equivalent cognitive impairment prior to and following treatment with mirabegron as well as change compared to the placebo group. To assess this primary objective, a test of equivalence will be performed using the two one-sided tests approach on change from visit 3 to visit 7 in MoCA total score within groups as well as between the two groups. Normality will be assessed by the Shapiro-Wilk test and the appropriate t-test or non-parametric alternative will be used. The equivalence range will be set at (-2, 2).

Other measures of cognitive impairment will follow similar analyses, but will not be considered the primary endpoint. Equivalence ranges will be determined for each measure based on available literature prior to data analysis.

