7.4.3 Summary of exploratory data

The exploratory objectives are to assess effects of mirabegron on orthostatic changes in blood pressure, depressive and anxiety symptomatology, excessive salivation, constipation and PD motor symptom severity in PD patients with OAB symptoms and CI. The related hypotheses are that mirabegron will not impact these symptoms. The goal is to demonstrate equivalent symptoms prior to and following treatment with mirabegron as well as change compared to the placebo group. Tests of equivalence will be performed using the two one-sided tests approach on change from visit 3 to visit 7 in related variables within groups as well as between the two groups. Equivalence ranges will be determined for each measure based on available literature prior to data analysis.

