APPENDIX XI: Constipation Questions

The following questions will be asked to establish the number of Rome II criteria each subject meets:

Over the last 2 weeks,

- 1. Did you have to strain at least 1 out of 4 times when having a bowel movement?
- 2. Did you have lumpy or hard stools at least 1 out of 4 times when having a bowel movement?
- 3. Did you have a sense of incomplete evacuation at least 1 out of 4 times when having a bowel movement?
- 4. Did you have a sensation of obstruction or blockage in your anal area at least 1 out of 4 time when having a bowel movement?
- 5. Did you have to use manual maneuvers to facilitate bowel movements at least 1 out of 4 times when having a bowel movement?
- 6. Did you have less than 3 bowel movements per week?

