APPENDIX XII: Unified Parkinson's Disease Rating Scale (UPDRS)

Unified Parkinson's Disease Rating Scale

i. Mentation, Behavior and Mood

1. Intellectual Impairment

- 0 = None
- 1 = Mild. Consistent forgetfulness with partial recollection of events and no other difficulties.
- 2 = Moderate memory loss, with disorientation and moderate difficulty handling complex problems. Mild but definite impairment of function at home with need of occasional prompting.
- 3 = Severe memory loss with disorientation for time and often to place. Severe impairment in handling problems.
- 4 = Severe memory loss with orientation preserved to person only. Unable to make judgements or solve problems. Requires much help with personal care. Cannot be left alone at all.

2. Thought Disorder [Due to dementia or drug intoxication.]

- 0 = None.
- 1 = Vivid dreaming.
- 2 = "Benign" hallucinations with insight retained.
- 3 = Occasional to frequent hallucinations or delusions; without insight; could interfere with daily activities.
- 4 = Persistent hallucinations, delusions, or florrid psychosis. Not able to care for self.

3. Depression

- 0 = Not present.
- 1 = Periods of sadness or guilt greater than normal, never sustained for days or weeks.
- 2 = Sustained depression (1 week or more).
- 3 = Sustained depression with vegetative symptoms (insomnia, anorexia, weight loss, loss of interest).
- 4 = Sustained depression with vegetative symptoms and suicidal thoughts or intent.

4. Motivation/initiative

- 0 = Normal.
- 1 = Less assertive than usual; more passive.
- 2 = Loss of initiative or disinterest in elective (non-routine) activities.
- $\mathbf{3} = \mathbf{Loss}$ of initiative or disinterest in day to day (routine) activities.
- 4 = Withdrawn, complete loss of motivation.

il. Activities of Daily Living [For both "on" and "off."]

5. Speech

- 0 = Normal.
- 1 = Mildly affected. No difficulty being understood.
- 2 = Moderately affected. Sometimes asked to repeat statements.
- 3 = Severely affected. Frequently asked to repeat statements. 4 = Unintelligible most of the time.

6. Salivation

- 0 = Normai.
- 1 = Slight but definite excess of saliva in mouth; may have nighttime drooling.
- 2 = Moderately excessive saliva; may have minimal drooling.
- 3 = Marked excess of saliva with some drooling.
- 4 = Marked drooling, requires constant tissue or handkerchief.

7. Swallowing

- 0 = Normal.
- 1 = Rare choking.
- 2 = Occasional choking.
- 3 = Requires soft food.

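### If the normality rule sends the salivation item to a Mann-Whitney equivalence test, the between-arm result is the same for every margin between 0 and 1 grade, and narrow margins can be declared met far too often

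*Combined protocol and SAP*

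**What the plan says.** Section 3.10.3.6 takes salivation from item 6 of the UPDRS: "It is rated 0-4 and can be self-administered". Appendix XII lists its five whole-number grades, ending at "4 = Marked drooling, requires constant tissue or handkerchief".

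For the exploratory outcomes, section 7.4.3 states: "Tests of equivalence will be performed using the two one-sided tests approach on change from visit 3 to visit 7". It asks for these tests "within groups as well as between the two groups". On the margin it says only: "Equivalence ranges will be determined for each measure based on available literature prior to data analysis".

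The method is spread over three other places. Section 7.4 says "Normality will be tested throughout using the Shapiro-Wilk test". Section 7.4.1, written for the MoCA, says "the appropriate t-test or non-parametric alternative will be used" and does not name the alternative. Section 7.4.2 names the Mann-Whitney-Wilcoxon test, but for the superiority comparison of bladder symptoms. Section 7.4.3 itself names neither a t-test nor a rank test.

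Constipation is in the same group of outcomes. Appendix XI describes a count: "The following questions will be asked to establish the number of Rome II criteria each subject meets". Section 3.10.3.4 describes establishing whether a subject meets the criteria, which is a yes/no status.

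**The concern.** In an equivalence test the margin carries the meaning: it states how large a difference would still count as no impact. A rank test moves one arm by the margin and asks whether the order of the observations then favours one side. Whole-number changes cannot be reordered by a shift smaller than one unit. A margin of 0.1 grade and a margin of 0.9 grade would therefore be judged by the same p-value. A narrow margin could be reported as met by a test that never used it, and a wide margin could be missed although the data support it.

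**Working it through.** **Inputs.** Grades 0–4 (3.10.3.6, Appendix XII). Planned arms of 20 and 10 (7.1). Significance level 0.05 without multiplicity adjustment (7.4), taken as 0.05 for each one-sided test. The documents give no salivation margin, distribution of changes or error rate, so there is no figure to reproduce. The distributions below are assumptions, and all 30 subjects are taken as analysed.

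**1. Algebra, between arms.** Let X be an active change, Y a placebo change and m the margin. The upper test counts pairs with X − m > Y. As X − Y is a whole number, for 0 < m < 1 this holds exactly when X − Y ≥ 1. No shifted active value ties with a placebo value, and ties within each arm are unaffected. Neither the count nor its variance depends on m. In 4,500 simulated trials, 11 margins from 0.01 to 0.99 gave identical p-values every time.

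**2. Worked example.** Active: 14 zeros, 3 at +1, 3 at −1 (mean 0). Placebo: 7 zeros, 2 at +1, 1 at −1 (mean +0.1). Observed difference −0.1.
- Pairs with X > Y: 3×8 + 14×1 = 38. Pairs with X < Y: 3×9 + 14×2 = 55. Expected count at no difference: 20×10/2 = 100.
- Ties of size 14, 3, 3, 7, 2, 1 give Σ(t³ − t) = 3,120. Variance = (200/12)(31 − 3,120/870) = 456.9, SD 21.4.
- z = (38 − 100 + 0.5)/21.4 = −2.88, p = 0.002; z = (55 − 100 + 0.5)/21.4 = −2.08, p = 0.0187. The larger p decides.
- Equivalence is declared with p = 0.0187 at every margin in (0, 1), even at 0.01, although the observed difference is 0.1. The p-value falls to 0.0004 at a margin of 1.0 and 0.00001 at 1.01.
- Welch on means: variances 6/19 = 0.316 and 2.9/9 = 0.322; SE = √(0.316/20 + 0.322/10) = 0.219; about 17.9 degrees of freedom; 90% CI −0.48 to 0.28. Equivalence fails at 0.25 and holds at 0.75, so the margin matters.

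**3. Would the rank branch be reached?** In the simulated active arms Shapiro-Wilk rejected in 93–100%. If the rule applies to this item and is run by arm, a rank test is close to certain.

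**4. False equivalence.** Placebo changes are −1, 0 or +1, symmetric. Each active subject moves up one grade with probability equal to the true difference, and the margin is set equal to that difference, so the rate should be at most 5%.

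| Placebo unchanged | 0.10 | 0.25 | 0.40 | 0.50 |
|---|---|---|---|---|
| 90% | 95% | 64% | 21% | 6% |
| 80% | 77% | 45% | 16% | 5% |
| 70% | 48% | 29% | 11% | 4% |
| 60% | 25% | 14% | 6% | 2.5% |
| 50% | 9% | 5% | 3% | 1% |
| 40% | 2% | 1% | 1% | 1% |

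Other assumed distributions with a 0.25 difference gave 14%, 31% and 55% at 70%, 80% and 90% unchanged. Welch under those gave 0.1–2.6%.

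**5. Wide margin.** With a true difference of 0.25 and a margin of 0.75, the rank rates stay at 14%, 31% and 55%. Equivalence is now the right answer, and Welch reaches it in 65%, 79% and 91%.

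**6. Within arm.** The signed-rank version is constant on (0, 0.5) and on (0.5, 1) but jumps at 0.5, where |0 − m| and |1 − m| change order. With 9 zeros, 8 at +1 and 3 at −1 (n = 20), p = 0.553 below 0.5, 0.095 at 0.5 and 0.0046 above. The 5% decision differed between margins 0.25 and 0.75 in 59–91% of simulated active arms.

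**7. Limits of the mean-based interval.** If 90% of placebo changes are zero, all ten are zero in 0.9¹⁰ = 35% of trials (0.8¹⁰ = 11% at 80%), and Welch then uses a placebo variance of zero. Suppose placebo never changes and 15% of active subjects worsen one grade, margin 0.15. Welch passes with 0 or 1 worsening: 0.85²⁰ + 20×0.15×0.85¹⁹ = 0.039 + 0.137 = 18% (rank test: 98%). Pooling raises the squared SE from s²/20 = 0.050s² to (19s²/28)(1/20 + 1/10) = 0.102s². One worsening then gives an upper limit of 0.05 + 1.70×√(0.102×0.050) = 0.17, which fails, leaving 0.85²⁰ = 3.9%. At 5% worsening and margin 0.05, all 20 active changes are zero in 0.95²⁰ = 36% of trials, and pooling does not help.

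**The case against.** **The test is inferred.** Section 7.4.3 names no method, the non-parametric clause belongs to the MoCA, and Mann-Whitney is named for a superiority test. This stands, and the conclusion is conditional on it. It is still the natural reading, because 7.4 applies the normality check throughout and no other rank test is named.

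**The margin is not set.** On a whole-grade item it may well be one grade or more, and then the result does depend on it. This stands too.

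**A reader might infer that the margin has no effect on any rank-based analysis of this item.** The documents do not support that. The plan also requires within-arm tests, where the usual signed-rank version changes at 0.5, and between arms the result changes at 1.

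**A reader might infer that false equivalence is inflated in general.** It is not. With 50% or fewer unchanged, the rate is near or below 5%, except about 9% at a margin of 0.10. At a margin of 0.50 it is about 6% or less throughout. The documents do not say which distribution will occur.

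**Constipation may not be affected.** The algebra carries over to a count, between consecutive whole numbers. A yes/no Rome II status would not be analysed this way, and the plan does not settle the scoring.

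**Conclusion.** The point holds in conditional form. If the Shapiro-Wilk rule is applied to the exploratory outcomes and the rank test is Mann-Whitney, the between-arm equivalence result for salivation is the same at every margin strictly between 0 and 1. That part is algebra and needs no distributional assumption.

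The size of the error does need one. With 70–90% of scores unchanged and a true difference and margin of 0.25, false equivalence is about 14–64%, depending on how the shift arises. At a margin of 0.75, true equivalence is missed more often than with a mean-based test.

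Salivation and constipation are exploratory outcomes in a 30-subject pilot, and no primary or secondary conclusion depends on them. The grade scale itself contains no error; the gap is in 7.4.3. Severity is minor.

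**What to change.** Amend 7.4.3 before unblinding:
- Do not let Shapiro-Wilk select the method for UPDRS-6, nor for constipation if a count is analysed. State which constipation score is used.
- Judge equivalence by the 90% confidence interval against the pre-set margin: the mean change within each arm, and the difference in mean change between arms. Use the Welch interval between arms, replaced by the pooled-variance interval when either arm has zero variance.
- Report the number of subjects per arm who worsen by at least one grade or criterion.

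This takes a sentence or two of analysis-plan wording and no new data. It has three costs. Equivalence is harder to declare at narrow margins: with no true difference, 80% unchanged and a margin of 0.25, about 9% of trials would succeed, against 87% with a rank test that ignores the margin. Grades are averaged as if evenly spaced. The interval can still be too narrow when almost all changes are zero, and has no width when all are, so such results should be read with the counts.
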